Cover Page

Official Protocol Title: Social Network Analysis and Renal Education to Promote Transplantation (SNARE Transplant)

Protocol for Social and Behavioral Protocol

Investigator: [name] M.D.

Document Last Edited: 4/3/2017

Approved by: Temple University Institutional Review Board

Protocol Number: 11648

Initial approval: 4/10/2017

Renewal approval: 4/9/2018

Abstract of the Study: Barriers to kidney transplantation exist among patients with ESRD on hemodialysis. The aim of this study is to use survey research to understand attitudes towards hemodialysis and kidney transplantation to identify barriers to living donor kidney transplantation among hemodialysis patients. The Dialysis Patient Transplant Questionnaire, or DPTQ, was designed to identify barriers to transplantation in a large urban, predominantly African American population of hemodialysis patients by surveying their perceptions of their health and quality of life, the availability of social and emotional support, and their experiences and attitudes regarding dialysis and kidney transplantation. Based on the preliminary results The major concerns were for the donor, asking for a kidney and their own health. These concerns are amenable to the COACH intervention. These studies focused on a poor and underserved black population, limiting their generalizability. Patients also rely on the hemodialysis clinic social networks for information regarding kidney transplantation. . We believe that hemodialysis social networks facilitate the spread of information and behaviors, and that using a targeted social network intervention will improve access to transplantation especially among women and minorities. Furthermore, patients subjective health will be correlated with objective measures obtained from patients medical record.

- 1) **Protocol Title:** Social Network Analysis and Renal Education to Promote Transplantation (SNARE Transplant) formerly: Survey of Dialysis Patients Regarding Their Views on Renal Transplantation
- 2) **Investigator:** [name] M.D.
- 3) **Objectives:** The aim of this study is to use survey research and the COACH (Communicating about Choices in Transplantation) to understand attitudes towards hemodialysis and kidney transplantation among hemodialysis patients and how the social networks do they form affect the diffusion of knowledge, attitudes, and behaviors towards transplantation. Lastly, patients subjective health will be correlated with objective measures obtained from patients medical record, to better understand patients health outcomes among hemodialysis patients.
- 4) **Rationale & Significance:** For patients with end stage renal disease, kidney transplant has been shown to have better outcomes than maintenance dialysis. A comparison of patients on the transplant waiting list those who eventually undergo transplantation have better long-term survival than those who do not get a transplant.^{1,2} In the United States African Americans have lower rates of renal transplant than whites,³ including living donor transplants. Previous studies have suggested that possible barriers to cadaveric donation include: denial of the need for transplantation, religion, fear of surgery, access to care, distrust of the medical system, less access to care, poor education, and racism.⁴⁻⁷ Barriers to living donation in African Americans have not been as well studied. The Dialysis Patient Transplant Questionnaire, or DPTQ, was designed to identify barriers to transplantation in a large urban, predominantly African American population of hemodialysis patients by surveying their perceptions of their health and quality of life, the availability of social and emotional support, and their experiences and

attitudes regarding dialysis and kidney transplantation. The questionnaire assesses three areas of interest; (1) demographic characteristics and the availability of social and emotional support; (2) self-reported health, quality of life, and the specific impact of kidney disease and its treatment; and (3) patient views of kidney transplantation, including self-reported listing status and perceived bias in transplantation allocation. (4) who patients talk to in the hemodialysis clinic, what they talk about and how often. Many of the items included in the DPTQ have been validated in hemodialysis and transplant populations⁸⁻¹⁵ including quality of life measures and independent predictors of mortality. Previous research has speculated that the social networks that patients form in the hemodialysis clinic may influence attitudes and behaviors towards transplant and may be amenable to social network interventions. Social network behavioral interventions in other fields¹⁶⁻²¹ have found that it may be better to target dense (clustered) networks than diffuse networks. As diffuse networks function as discussion networks and can be more effective in changing behavior than diffuse networks which function as advice networks and are better at spreading novel information through a central person¹⁹⁻²¹. Once patients social networks have been mapped, we will assign every HD clinic shift to one of the two targeting strategies based on social network attributes for the COACH intervention. We will measure the spread of information, attitudes, and behaviors by comparing the targeted patients to those that they refer, as well as the other patients on their shift. The COACH was specifically designed to educate patients on kidney disease and communication skills to approach other people about potential donation.

- 5) **Resources and Setting:** All participants collecting and entering data will be IRB and HIPAA trained. All data will be stored on a HIPPA secure, password/firewall protected computer in an office that is locked. Once the data has been collected it will be de-identified for analysis. The participating facilities are medical clinics with standard HIPPA policies. The following facilities are: DCI Philadelphia [name] DCI North Brunswick [name]. Patients are no longer going to be enrolled at the following sites: Fresenius Dialysis/Temple Joint Venture [name], Fresenius Dialysis/Temple Joint Venture Port Richmond, [name], Temple Abdominal Organ Transplant Clinic [name], however data collection and analysis is ongoing.
- 6) **Prior Approvals:** Approval has been granted by the medical directors of all of the aforementioned facilities.
- 7) **Study Design:**
 - a. **Recruitment methods:** Convenience sample of English speaking patients greater than 18 years old while receiving hemodialysis for ESRD, who are able to give consent. This population is over 500 patients. Patients will be approached by a survey researcher while getting their hemodialysis

treatment. There will be a ten dollar gift card as compensation for participating in the survey. There will be no advertisement for the study.

- b. **Inclusion/Exclusion Criteria:** All patients over the age of 18 who are receiving hemodialysis for ESRD are eligible to participate in the initial survey. Patients will be excluded if they are under the age of 18, or unable to consent for other reasons (i.e. dementia). Only transplant eligible patients may participate in the COACH intervention. Patients who have not been referred for kidney transplantation will be evaluated for transplant eligibility via chart review by a study transplant nephrologist for transplant candidacy. If the patient is eligible for transplant but not referred, the transplant nephrologist will discuss with the primary nephrologist if the participant is an appropriate candidate and reasons they have not been referred. We will defer the transplant referral to the attending nephrologist. Our major exclusion criteria are nursing home resident, >79 years of age, active or recent malignancy, inoperable coronary artery disease, or comorbid illness that will make it unlikely that the patient will survive >3 years after transplant.
- c. **Study Timelines:** The proposed research combines both a longitudinal observational cohort study to examine the structure of HD clinic social networks and a targeted transplant education intervention (COACH) trial to test the role of the network in the dissemination of knowledge, attitude, and behaviors with the overall goal of improving access to kidney transplantation. Data will be analyzed yearly and modifications and interventions will be made accordingly.
- d. **Study Procedure and Data Analysis:**
 - i. After consent has been obtained the patient will be given a baseline survey. This survey will then be repeated annually for the next 2 years. Three surveys in total. If the patient is chosen for the COACH intervention (see sections d.iii-v), they will also receive an additional survey post-intervention. The patient has the option of completing the survey themselves or completing it with a trained survey researcher. Clinic staff will also participate in a modified version of the survey to assess their attitudes towards HD and kidney transplantation.
 - ii. In addition to surveys, the clinic staff will be trained to observe which patients talk with whom, as well as, the frequency and approximate duration of the conversation. The staff will be instructed to continue to assign seating based on clinical necessity and patient preference. Research staff, while they are performing the surveys or the COACH intervention, will also make and record observed patient interactions. Furthermore seating assignments

will also be collected. This data will be coded, patients will be de-identified for the analysis.

- iii. COACH is a behavioral communication intervention designed specifically for ESRD patients pursuing kidney transplantation. The COACH program (appendix) consists of four modules: 1) Kidney transplant options, 2) Discussing your transplant options, 3) Requesting living donation, and 4) Maintaining positive relationships. The content and teaching strategies were guided by the concepts of social cognitive theory as well as principles of adult learning and communication skills²²⁻²⁵. Another study coordinator will conduct the intervention in four, face to face, one hour sessions in the HD clinic. Patients will receive the accompanying handbook and video for the COACH intervention.
- iv. Using the data collected from the original survey and social network analysis, we will randomly select one transplant eligible patient (based on network attribute (most-clustered or most-central) per shift to participate in the COACH intervention.
- v. We propose a pre-post design to assess the impact of the COACH education on patients' transplant-related knowledge and behaviors. Before administering the COACH education, we will survey targeted patients to assess changes in knowledge and behaviors towards transplant from the baseline survey. As another measure of the impact of the COACH intervention, patients not receiving the intervention will serve as controls and will be surveyed along with those receiving the intervention; we will then assess within and between group differences in transplant-related knowledge and behaviors. To assess the dissemination of information contained in the COACH intervention, all patients will be surveyed at 3-months post-intervention. The follow-up surveys will determine the sources of these changes (eg. self-reading after the survey, the COACH intervention, or discussing with other patients). Finally, during Year 4, one year post-intervention, a final survey will be administered to all the patients in both clinics to assess retention of information and change in attitudes and behaviors of those who participated in COACH and the spread of information and behaviors to the patients who were not targeted.
- vi. The medical information collected is age, insurance status, ESRD diagnosis, vascular access. Medical comorbidities: congestive heart failure, peripheral vascular disease, malignancy. Mental Health, Substance Abuse, and HIV information is not collected. If the patient has ESRD from HIV the diagnosis is coded as glomerulonephritis a common and non-specific cause of ESRD.

Phosphate binding medication, Vitamin-D, and Calcimetic prescribing information is collected. Laboratory data includes basic metabolic panel, phosphorus, cbc, iron studies, hepatic function, cholesterol. Data collected will be analyzed to better understand barriers to transplantation and compare self-reported (survey) health data to laboratory data. All data is entered in an Excel spreadsheet and analyzed in SPSS 17.0, using descriptive statistics, chi-square test of association and t-tests. Time series analysis will be done in MathWorks MATLAB software. A p-value of less than 0.05 will be deemed significant.

- e. **Withdrawal of Subjects:** Patients may withdraw at anytime, this will be as a result of the patient transferring out of the clinic. Once, the patient withdraws they can contact the survey researcher or the PI and data will stop being collected.
 - f. **Privacy & Confidentiality:** All documents and information pertaining to this research study will be kept confidential in accordance with applicable, federal, state, and local laws and regulations. If any data is published the patient will not be identified by name. All participants collecting and entering data will be IRB and HIPAA trained. All data will be stored on a HIPAA secure, password/firewall protected computer in an office that is locked. Paper records will be kept in a locked file cabinet in a locked office. Once the data has been collected it will be de-identified for analysis. The participating facilities are medical clinics with standard HIPAA policies. The survey is anonymous, and the patients' individual response will not be shared with the treating physician or staff. Patients will also sign a HIPAA secure discussing protected health information. Personal health information will be deleted 5 years after the completion of the study.
- 8) **Risks to Subjects:** There are no invasive procedures involved with this study, however, patients are given 24 hour contact information for the study coordinator as well as the study director if they feel they have experienced any adverse events or have any further questions. The COACH intervention was specifically designed to minimize the stress associated with asking for a living donor kidney transplant. The patients' individual response will not be shared with the treating physician or staff. As we are performing a social network study we will not disclose to other patients whether they have been identified in another patients social network, nor other patients transplant eligibility. Furthermore, the subjects' surveys are identified by study ID number and not by name. All data is kept on firewall protected HIPAA compliant computer in an office that is locked when not in use.

9) **Potential Benefits:** There are no immediate benefits, however, the benefit of this study is to better identify barriers to kidney transplantation and help create an intervention to decrease the disparities in kidney transplantation.

10) **Costs to Subjects:** None

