Interestingly, 39% of the patients surveyed with the DPTQ reported linking the social aspect of HD. Based on these results, we performed a three-year longitudinal, prospective observational study on the formation of social networks in a new HD clinic and examined the networks' effects on kidney transplantation¹. Forty six racially and ethnically diverse patients (24% White, 33 % Black, 30% Hispanic, and 13% Multiethnic) were enrolled and studied with repeated survey measures and clinical observations. Thirty one patients (67%) were observed interacting with each other and participating in the HD social network (Appendix, Figure2). Gender, not race, was associated with participation in the social network. Almost all (91%) transplant eligible males were linked to other patients compared to 56.3% of the eligible women ($p=0.02$). Patients participating in the social network completed a median of 50% (Interquartile Range (IQR) 33 – 96%) of steps towards transplant compared to a median of 0% (IQR 0 – 23%) of those who did not ($p<0.001$). On sub-network analysis, patients who participated in health discussions with other patients, as well as those who received a kidney transplant had dense, sub-networks with higher clustering coefficients with the a mean of 50% of the patients in their network being interconnected with each other (0.52 ± 0.35 vs. 0.14 ± 0.30 , $p=0.0002$). Women, who participated in the social network, discussed their health more than men (90% vs 45% $p=0.02$) and tended to have a higher clustering coefficient (0.623 vs 0.356 , $p=0.07$). On further sub-network analysis, the percent of the work-up completed by a patient correlated with the steps completed by members of their sub-network ($R^2 = 0.42$, $p = 0.02$) and for patients who were interested but had not started the transplant process (step 2, Table 4), the clustering coefficients predicted the percentage of transplant steps completed ($\beta=2.23$; [95% CI], 0.16-4.29, $p = 0.003$, $r^2=0.19$). Lastly patients, who received a kidney transplant during the study had denser networks (0.71 ± 0.36 vs. 0.23 ± 0.32 , $p= 0.002$). These dense, highly connected networks as measured by the

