AIM3: Compare and contrast the diffusion of knowledge, attitudes, and behaviors regarding transplantation through HD social networks by targeting either the most central or the most clustered members of the network to disseminate a transplant education intervention. **H3:** Targeting patients with high clustering coefficients will be the most effective method for the spread of knowledge and favorable attitudes toward transplantation, and completing steps toward transplantation as compared to targeting by centrality.

Rationale: Previous studies have shown that barriers to transplantation tend to be less about information but rather behaviors related to completing the transplant steps^{1,2,4,13}, thus dense social networks are likely to be more effective in changing behavior and participating in a social network than diffuse networks, which are more effective at spreading novel information³²⁻³⁴.

Patient Recruitment, Eligibility, and Retention AIM 3: One year after the initial survey, we will use a targeted network intervention to measure the spread of information, attitudes, and behaviors. We will target transplant eligible patients based on their clustering coefficient or their betweenness centrality to participate in the COACH education using data collected in AIMS 1 and 2.

Recruitment Goals: Based on previous research^{1,4}, we anticipate approximately half the patients would be eligible for a kidney transplant but not on the list. If 250 patients participate in **AIM 1 and 2**, then at least 125, or approximately 10 patients per shift will be eligible for the intervention. The intervention will target either the two most central transplant eligible patients or the two most clustered patients to participate in the COACH education. As this is a social network intervention, although we are targeting only two patients per shift, all the patients on that shift are considered exposed to the COACH education. To prevent selecting a patient that is both relatively central and clustered, the patients selected by centrality will have a centrality greater than 1 standard deviation (SD) from the mean and a clustering less than 1 SD from the mean. Conversely, the

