Staggered Surveys: We propose a pre-post design to assess the impact of the COACH education on patients' transplant-related knowledge and behaviors. Before administering the COACH education, we will survey targeted patients to assess changes in knowledge and behaviors towards transplant from the baseline survey. As another measure of the impact of the COACH intervention, patients not receiving the intervention will serve as controls and will be surveyed along with those receiving the intervention; we will then assess within and between group differences in transplant-related knowledge and behaviors. To assess the dissemination of information contained in the COACH intervention, all patients will be surveyed at 3-months post-intervention. The follow-up surveys will determine the sources of these changes (eg. self-reading after the survey, the COACH intervention, or discussing with other patients). Finally, during Year 4, one year post-intervention, a final survey will be administered to the all the patients in both clinics to assess retention of information and change in attitudes and behaviors of those who participated in COACH and the spread of information and behaviors to the patients who were not targeted.

Clinical Data: In addition to the survey data, we will collect patient transplant listing status, living donor evaluations from participants' respective transplant centers.

Analytic plan AIM3: To test **H3** we will assess the successful spread of the intervention by evaluating the difference in the primary outcome of completion of steps toward transplantation between patients being exposed via the most clustered (Cluster) members versus the most central (Central). We will use repeated surveys to measure our secondary outcomes include change in knowledge, attitudes, behaviors of the patients either directly exposed to the intervention or those who were exposed indirectly through the social network.

Primary Outcomes: 1) Differences in patient knowledge, 2) Differences in transplant steps completed

Secondary Outcomes: 1) Completion of transplant work-up, 2) Asking for a living donor

Independent Variables: Intervention assignment to Cluster or Central

Covariates: Age, Marital Status, insurance, transplant eligibility, HD shift, HD Clinic, network attributes

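### On Cluster shifts, trained patients are picked for a trait the SAP links to step progress, so comparing them with shift-mates could show about a 1-step gap with no COACH effect

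*Protocol*

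**What the plan says.** **Contrasts.** Protocol section 4 (Rationale & Significance) measures spread "by comparing the targeted patients to those that they refer, as well as the other patients on their shift". SAP Aim 3, Staggered Surveys, states that "patients not receiving the intervention will serve as controls and will be surveyed along with those receiving the intervention", with differences assessed within and between groups. It also uses the final survey to assess "the spread of information and behaviors to the patients who were not targeted". The SAP's Analytic plan AIM3 takes its secondary outcomes in "patients either directly exposed to the intervention or those who were exposed indirectly through the social network".

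**Selection.** SAP Aim 3, Recruitment Goals: "The intervention will target either the two most central transplant eligible patients or the two most clustered patients to participate in the COACH education". Limits of 1 SD on each measure are meant to keep the two kinds of target apart. Protocol 7.d.iv has one target instead: "we will randomly select one transplant eligible patient (based on network attribute (most-clustered or most-central) per shift".

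**Prior evidence.** SAP Preliminary Results reports that, among patients who were interested but had not started the process, "the clustering coefficients predicted the percentage of transplant steps completed" (r² = 0.19). Patients transplanted during that study had mean clustering of 0.71, against 0.23 in the others.

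**Named test.** SAP Aim 3, Exposure and Analysis, compares everyone on Cluster shifts with everyone on Central shifts by a t-test on changes. Network attributes are listed as covariates, but no model using them is written for the trained v untrained or untargeted contrasts.

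**The concern.** Trained and untrained patients on a Cluster shift differ by design in clustering. If clustering predicts progress, the trained patients move ahead whether or not COACH works. Analysing change from baseline does not remove this, because the reported association comes from patients at a common starting step and so concerns progress itself.

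The same selection affects the untargeted groups. On Cluster shifts the most clustered eligible patients are taken out of the untargeted group, and on Central shifts most of them stay in. Untargeted patients in the two arms then differ before any COACH content spreads.

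At stake is the reading of COACH's direct effect and of its spread. The first would be flattered on Cluster shifts. The second would be understated for Cluster.

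**Working it through.** **The plan's own figure.** The SAP's effect size of 1.06 with 15 per arm, two-sided α = 0.05, gives 80.0% power, so its total of 30 reproduces. With 60 per arm and 1 step (d = 0.53) power is 82.1%. The 1.06 does not follow from the quoted 7 (SD 1.5) v 5 (SD 1.7): the pooled SD is √((1.5² + 1.7²)/2) = 1.60, and 2/1.60 = 1.25. An effect size of 1.06 implies SD 2/1.06 = 1.89. I use SD 1.6 and show the effect of 1.5 and 1.89.

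**Inputs.**
- r between clustering and steps: √0.19 = 0.436. The quoted CI of 0.16 to 4.29 implies SE (4.29 − 0.16)/3.92 = 1.05, z = 2.23/1.05 = 2.12 and p of about 0.034, not the stated 0.003. I therefore also use r = 0.2 as an assumption.
- About 10 eligible patients per shift, 12 shifts, six per arm (SAP).
- Targets per shift: two (SAP) or one (Protocol).
- Correlation of clustering with centrality: 0.024 (SAP).
- Assumed: normally distributed attributes and no shift effect.

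**By formula.** Of 10 standard normal values, the top two average 1.27 and the other eight −0.32, a gap of 1.59.
- Trained v shift-mates, Cluster: r × gap × SD = 0.436 × 1.59 × 1.6 = 1.11 steps. It is 1.04 at SD 1.5, 1.31 at SD 1.89, and 0.2 × 1.59 × 1.6 = 0.51 at r = 0.2.
- Untargeted, Cluster minus Central: −0.436 × 0.32 × 1.6 = −0.22 step, or −0.10 at r = 0.2.

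**By simulation.** 4,000 runs per setting, SD 1.6, no COACH effect, no spread of COACH content. Ranges cover one or two targets per shift, with and without a cap of +1 SD on the other attribute. Rejection is at two-sided 0.05.

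| Contrast | r = 0.436: steps | Rejection | r = 0.2: steps | Rejection |
|---|---|---|---|---|
| Trained v others, Cluster shifts | +0.99 to +1.18 | 35–59% | +0.44 to +0.53 | 11–16% |
| Trained v others, Central shifts | −0.23 to +0.03 | 6–7% | −0.10 to +0.02 | about 6% |
| Untargeted, Cluster minus Central | −0.11 to −0.24 | 7–12% | −0.05 to −0.11 | 5–7% |
| Whole shift, Cluster minus Central | 0.00 | 5% | 0.00 | 5% |

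With r = 0 every contrast stays near 5%. If targets also had to be below the mean on the other measure, the Cluster gap with two targets would be about 0.68 step, with 25% rejection.

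**The remedy under the same null.** Listed Cluster targets v would-be Cluster targets on Central shifts: 0.00 ± 0.01 step, about 5% rejection. Patients on neither list, between arms: 0.00 to 0.01 step, about 5%. Linear adjustment for clustering also removed the untargeted bias.

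**The case against.** The strongest reply is that H3's named test is untouched. It keeps everyone on the shift, trained or not, and the check confirms no bias. That stands. A reader might infer that the primary comparison is compromised, and the documents do not support that.

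A reader might also infer that both strategies are affected. The documents link clustering to steps but give no such link for betweenness centrality, and report the two as uncorrelated. A positive gap on Central shifts would have to come from taking part in the network at all (median 50% v 0% of steps), not from the targeting attribute.

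The untargeted comparison between arms is implied by Staggered Surveys and not written as a test, so its bias is conditional on someone running it. Nor is adjustment hopeless. Within one shift there is little overlap in the attribute, but across arms the Central shifts hold untrained, highly clustered patients.

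The size rests on one association from a subgroup of a 46-patient study with an internally inconsistent p-value, hence the lower r. The documents report no association between clustering and knowledge, the other primary outcome, so nothing is claimed for it.

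The plan also has a pre-COACH survey of targeted patients, network-distance analyses and a model with demographic, social and shift terms. These could help, but none is specified as the adjustment for these contrasts.

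**Conclusion.** The concern holds for the trained v untrained comparison on Cluster shifts. With no COACH effect, the expected lead in steps is about 1.0 to 1.2 at r = 0.44 and about 0.5 at r = 0.2, against the 1 step the trial is powered for. An untargeted comparison between arms would be biased against Cluster by about 0.1 to 0.25 step, or 0.05 to 0.12 at r = 0.2. The whole-shift primary test is sound on this point.

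The figures assume about 10 eligible patients per shift, SD 1.6, normal attributes and comparison with eligible shift-mates. If ineligible patients count among the others on the shift, eligibility adds further confounding. No COACH effect here means no effect of COACH content. The earlier association may itself reflect natural spread, which the SAP says its observational aims cannot separate from like-minded patients grouping together.

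**What to change.** Before COACH starts, apply both selection rules to all 12 shifts and lock the lists. Each shift then has its actual targets and the would-be targets of the other strategy.

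- **Spread.** Compare arms only among patients on neither list, or adjust the untargeted contrast for baseline clustering and centrality, which are already listed as covariates. Cost of the first option: about two more patients per shift, or roughly 36 instead of 48 per arm (six shifts × 6 instead of × 8).
- **Effect on trained patients.** Compare listed Cluster targets on Cluster shifts with would-be Cluster targets on Central shifts, and the reverse for Central, in place of shift-mates. Analyse patients as first listed, whether or not they accept COACH. The SAP replaces refusers, and the would-be group includes people who would have refused.

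The second comparison is weak. It has about 12 v 12 patients, giving about 24 to 35% power for 1 step (SD 1.89 to 1.5), or 13 to 18% with one target per shift. It is a between-shift contrast, and its comparators are themselves exposed to spread. Report it as an estimate with a confidence interval, not as a test of COACH.

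Two points need settling so that the lists can be drawn up. The Protocol and SAP must agree on the number of targets. The SD limits must also yield candidates: read literally and under normality, about 0.1587 × 0.1587 × 10 = 0.25 Cluster candidates and 0.1587 × 0.8413 × 10 = 1.3 Central candidates qualify per 10 eligible patients. Otherwise the change costs SAP wording and one extra list from measures Aim 1 already computes.
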